4.8.2.3 Mortality

Mortality rate up to study day 30 and day 90 will be summarized. These will be tabulated by primary cause of death. Deaths that occurred after the Day 90 visit date (up to 120 days since randomization) but captured in the database (e.g., as an outcome of an ongoing SAE) will not be included in the safety summaries unless the event is believed to be related with study treatment. All known deaths will be listed.

Details of any deaths will be presented in the form of individual patient listings.

4.8.2.4 Parenchymal Hematoma Type 2

The proportion of patients with PH2 intracranial hemorrhage within 72-96 hours follow-up visit will be summarized by treatment group.

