5.3.5.8 Deaths

For this protocol, mortality rate is a safety endpoint. All deaths that occur during the adverse event reporting period, regardless of relationship to study drug, must be recorded on the Adverse Event eCRF and immediately reported to the Sponsor (i.e. no more than 24 hours after learning of the event; see Section 5.4.2). The *i*DMC will monitor the frequency of deaths from all causes.

When reporting a death, the event or condition that caused or contributed to the fatal outcome should be recorded as the single medical concept on the Adverse Event eCRF. Generally, only one such event should be reported. If the cause of death is unknown and cannot be ascertained at the time of reporting, "**unexplained death**" should be recorded on the Adverse Event eCRF. If the cause of death later becomes available (e.g., after autopsy), "unexplained death" should be replaced by the established cause of death. The term "**sudden death**" should not be used unless combined with the presumed cause of death (e.g., "sudden cardiac death").

Deaths that occur after the adverse event reporting period should be reported as described in Section 5.6.

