AIS=acute ischemic stroke; CBC=complete blood count; CT=computed tomography; DWI=diffusion-weighted imaging; eCRF=electronic Case Report Form; FLAIR=fluid-attenuated inversion recovery; GOS=Glasgow Outcome Scale; GRE=gradient recalled echo; IV=intravenous; MRA=magnetic resonance angiography; MRI=magnetic resonance imaging; MRP=magnetic resonance perfusion; mRS=modified Rankin Scale; NIHSS=National Institutes of Health Stroke Scale; sICH=symptomatic intracranial hemorrhage; SOC=standard of care.

- ^a Patients should return to the clinic for follow-up 30 and 90 days after treatment. At Day 90, patients should have the study completion visit. If an in-person visit is infeasible, *only* the mRS should be performed by telephone. *All questionnaires can be collected by telemedicine except the Neuro-QoL.*
- ^b Medical history, including clinically significant diseases, surgeries, cancer history (including prior cancer therapies and procedures), reproductive status, smoking history, and use of alcohol and drugs of abuse, will be recorded at baseline. Demographic data will include age, sex, self-reported race/ethnicity, and veteran status.
- ^c Vital signs will include measurements of respiratory rate, pulse rate, and systolic and diastolic blood pressure, and temperature. Temperature will be required prior to randomization and will be performed with subsequent frequency per SOC. The frequency of respiratory rate, pulse rate, systolic and diastolic blood pressure measurements should reflect post-IV thrombolytic monitoring in AIS per SOC.
- ^d Patients should be weighed before randomization. Glucose (finger stick or blood draw) and coagulation tests (INR, aPTT, PT [only if the patient is taking an anticoagulant]) should be done. Results are required prior to randomization.
- ^e Platelet count results must be checked prior to randomization in patients with suspected coagulopathy. Electrolytes will also be collected. All other CBC and electrolyte results are NOT required prior to randomization.
- ^f All women of childbearing potential will have a urine/serum pregnancy test at screening. If a urine pregnancy test is positive, it must be confirmed by a serum pregnancy test.
- ^g A pre-stroke mRS will be estimated a baseline. Thirty and 90 days after treatment, patients should be evaluated using mRS preferably in the clinic; if an in-person visit is not feasible, the patient can be evaluated by telephone ([Appendix 2](#)).

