2.2.5 Safety Endpoints

The safety endpoints include:

- Incidence of symptomatic intracranial hemorrhage (sICH) within 36 hours.
- Incidence and severity of adverse events (AE).
- Mortality rate up to Day 30 and Day 90.
- Proportion of patients with parenchymal hematoma type 2 (PH2) at the 72-96 hours visit.

Further detail is described in Section 4.8.

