4.6.2.7 Glasgow Outcome Scale

The GOS is a scale used to assess recovery of patients with brain damage. The scale has 5 categories, with scale ranging from 1 (death) to 5 (good recovery). For the purpose of analysis, the scale will be reversed so that 1=good recovery and 5=death, to align with the common practice in clinical trials.

If death occurs prior to Day 90, GOS will be considered available and will be set to 5.

The proportion of patients with good recovery, i.e., rescaled GOS score = 1, at Day 90 will be analyzed using logistic regression adjusted as specified in Section 4.6. Observed counts and percentages for tenecteplase and placebo arms, and model based odds ratio, corresponding Wald 95% CI and p-value will be produced.

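### SAP 4.8.2.3 contradicts itself: mortality runs to study day 90, yet known unrelated deaths after an early Day 90 visit are excluded, even when they occur by Day 90

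*SAP*

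**What the plan says.** The endpoint in SAP 2.2.5 is "Mortality rate up to Day 30 and Day 90", with no condition on cause. Protocol 5.3.5.8 states "For this protocol, mortality rate is a safety endpoint", requires deaths in the adverse event reporting period to be recorded whatever their relationship to study drug, and has the iDMC follow deaths from all causes.

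SAP 4.8.2.3 begins in the same terms: "Mortality rate up to study day 30 and day 90 will be summarized". It then sets a second cut. "Deaths that occurred after the Day 90 visit date (up to 120 days since randomization) but captured in the database" are the subject of a rule that they "will not be included in the safety summaries unless the event is believed to be related with study treatment". It adds "All known deaths will be listed".

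The schedule of activities (Protocol Appendix 1, repeated in SAP Appendix 2) puts the last visit at 90 ± 14 days. Footnote a reads "At Day 90, patients should have the study completion visit".

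SAP 4.6.3.8 (overall survival, exploratory) counts deaths up to the Day 90 visit or within 120 days of randomization. It adds later deaths that have a related fatal adverse event, and censors patients not known to have died by the visit at their last study assessment.

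**The concern.** The first sentence of 4.8.2.3 cuts by study day. The later one cuts by visit date and judged cause. They disagree for any patient whose visit comes before Day 90 and who then dies on or before Day 90 of a cause judged unrelated. Take a visit on Day 77 and an unrelated death on Day 85: the first sentence counts the death and the later one removes it.

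An all-cause mortality rate to a fixed day is a basic safety measure for a thrombolytic. It should not depend on when the visit happened to be booked or on an opinion about cause. The listing shows the death but does not correct the rate by arm. A programmer given both sentences has to choose between them, and the choice should not be left until treatment codes are known.

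**Working it through.** **1. Width of the gap.** The earliest scheduled visit is 90 − 14 = Day 76 and the latest is 90 + 14 = Day 104. A patient seen on Day 76 has up to 14 days before Day 90 in which a known unrelated death would be left out. A patient seen on or after Day 90 has none. The reference to 120 days sets only an upper limit; nothing sets a lower limit at Day 90.

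**2. Scale.** The documents give no mortality count to reproduce, so this is an illustration.

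Inputs from the documents: 228 patients per arm; deaths by Day 90 of 12% (tenecteplase) and 18% (placebo), the mRS 6 column of Protocol Table 7 and SAP Table 1.

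- Expected deaths: 228 × 0.12 + 228 × 0.18 = 27.36 + 41.04 = 68.4.
- Expected alive: 228 × 0.88 + 228 × 0.82 = 200.64 + 186.96 = 387.6.

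Assumptions: visits uniform on Days 76 to 104; a late death rate of 1%, 2% or 3% per month; all such deaths judged unrelated.

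- Mean gap = (14² / 2) / 28 = 3.5 days.
- Person-days in the gap = 387.6 × 3.5 = 1,357.
- Daily hazard = −ln(1 − h) / 30.44.
- Expected deaths in the gap = 1,357 × daily hazard; chance of at least one = 1 − exp(−expected).

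| Monthly rate h (assumed) | Both arms | Tenecteplase | Placebo | Chance of at least one | Both arms, 25% captured |
|---|---|---|---|---|---|
| 1% | 0.45 | 0.23 | 0.22 | 36% | 0.11 |
| 2% | 0.90 | 0.47 | 0.43 | 59% | 0.23 |
| 3% | 1.36 | 0.70 | 0.65 | 74% | 0.34 |

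Per arm this is 0.1 to 0.3 percentage points (0.23 / 228 to 0.70 / 228). If visits were uniform on Days 76 to 90, the mean gap is 7 days and the figures double, to 0.90 to 2.71.

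The last column is there because only deaths that reach the database can be restored; 25% is an assumed capture rate.

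**3. Cross-check with another late-death model.** Suppose 15%, 30% or 67% of the 68.4 deaths fall evenly over Days 30 to 90. Then deaths in the gap = 68.4 × share × 3.5 / 60 = 0.6, 1.2 or 2.7. The order of magnitude is the same.

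**4. Survival (SAP 4.6.3.8).** Simulated patients were alive at Day 76, with the same hazards and visits. Deaths were counted to Day 120 and survivors were censored at the visit. Multiplied by 0.85 (the average proportion alive), the Kaplan-Meier estimate at Day 90 is too low by 0.14 to 0.42 points if every later death is found. At 25% capture it is too low by about a quarter of that, 0.04 to 0.10. If follow-up ends at the same point for deaths and survivors, the bias is below 0.01 points.

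**The case against.** The strongest reply is that 4.8.2.3 starts with a study-day cut, and that the later sentence, with its 120-day limit and its example of a death emerging from an ongoing serious event, was meant for deaths after study completion. That is probably the intent. But the completion visit can itself precede Day 90, and the wording has no clause to protect deaths on or before that day. If the first sentence governs, the later one still has to be amended.

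A second reply is that the filter follows data collection. After the reporting period, Protocol 5.6 asks for notification only of serious events believed related, so unrelated deaths are found by chance. This stands as a limit on what can be recovered. Because the reporting period can be read as ending at the completion visit, no conflict with the protocol is claimed. It does not justify dropping a death that is already known.

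Some stronger readings are tempting, and the documents do not support them:

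- **A gap from Day 61.** SAP Table 2 accepts Day 90 assessments from Day 61, but those windows apply to clinical efficacy assessments. They do not define when the completion visit takes place.
- **The same patient dead for GOS but alive in the mortality table.** SAP 4.6.2.7 says "If death occurs prior to Day 90, GOS will be considered available and will be set to 5". Day 90 there can be read as the visit label of Table 2, in which case the discrepancy disappears.
- **An error in the primary endpoint.** SAP 4.9.1.1 deals with a missing Day 90 mRS and does not settle the case of an observed score inside the window. Extending the mortality rule to mRS could replace an observed score with 6, so it is not proposed.
- **A survival bias of 0.42 points.** That is the top of the range and requires every later death to be found. The 120-day clause can also be read as a cut-off for patients without a Day 90 visit.

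**Conclusion.** The point holds as an internal contradiction in SAP 4.8.2.3. Taken literally, the later sentence removes known unrelated deaths between an early visit and Day 90 from the all-cause Day 90 rate.

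The expected loss is about one death or fewer over both arms in most of the range examined, split almost evenly between arms. The size rests on assumed visit timing, late death rate, capture and relatedness, none of which the documents give; treating all these deaths as unrelated makes the figures upper values on that count. The contradiction does not depend on these assumptions. SAP 4.8 plans no safety hypothesis test, every known death is listed, and the primary analysis is unaffected.

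The survival issue is secondary. Follow-up after the visit depends on outcome and, through the add-back, on judged cause, but the endpoint is exploratory and the bias is a fraction of a point. The correction should be made because mortality is a named safety endpoint and the change is cheap.

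**What to change.** **SAP 4.8.2.3.** Count every known death with study day ≤ 30 and ≤ 90 from randomization, whatever the visit date or judged relatedness. List later deaths separately, with cause and relatedness. Report by arm how many patients have unknown vital status between an early visit and Day 90, and state that the count is then a lower bound.

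**SAP 4.6.3.8 (exploratory).** Use one end of follow-up for deaths and survivors alike: Day 90, or last contact if earlier. Delete the 120-day clause and the related-death add-back. Counting deaths found after last contact while survivors stop there would bring the bias back. Any bias figure should be shown over a range of capture.

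**Cost.** One sentence replaced in 4.8.2.3 plus the vital-status count, and about two sentences in 4.6.3.8. Deaths already in the database need no new data. Vital status between an early completion visit and Day 90 may not have been collected, which is why the number unknown has to be reported. The mRS rules in 4.6.1 and 4.9.1.1 stay as they are.

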4.8.3 Laboratory Data

Baseline lab results will be converted to International System of Units (SI) and summarized by treatment group.

4.8.4 Vital Signs

Baseline vital signs, including pulse rate, respiratory rate, weight, temperature, and systolic/diastolic blood pressure, will be converted to SI units and summarized by treatment group.

4.9 MISSING DATA

Missing data will be maintained as missing in the analysis datasets, unless specified otherwise. For variables where missing data are imputed, the analysis dataset will contain a new record with the imputed value and the original variable value will be maintained as missing.

4.9.1 mRS

For patients with no post-baseline mRS assessments, missing post-baseline mRS scores will not be imputed and these patients will be excluded from all mRS related analyses.

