4.6 EFFICACY ANALYSIS

Efficacy analyses will be performed using the ITT population with patients grouped according to treatment assigned at randomization. Available data regardless of adherence to the protocol will be included in the efficacy analyses; this includes data from patients who discontinued prematurely from the study.

Deviation from the AHA/ASA treatment guidelines for standard of care (i.e. mechanical thrombectomy [MT] is planned for the patient but not performed due to various reasons) is considered an intercurrent event in this study. COVID-19 infections are considered another type of intercurrent event. COVID-19 infections during the follow-up period will be captured as AEs. In efficacy analyses, treatment policy strategy will be applied to both COVID-19 and non-COVID-19 intercurrent events. That is, all collected data will be used regardless of the occurrence of these intercurrent events.

Visit windows will be derived according to [Table 2](#) and applied for all clinical efficacy assessments. If there are multiple assessments within the same window, the one closest to the target time point will be used. Assessments that are outside of the defined windows will not be used in analysis, except they may provide a value for the last observation carried forward (LOCF) imputation in the case of mRS (see Section [4.9.1.1](#)).

Table 2 Definition of Visit Windows

Visit	Target Time	Window: mRS, GOS, BI, Neuro-QoL*	Window: NIHSS	Window: imaging
24 hours	24 hours	N/A	18 to 30 hours	18 to 30 hours
72-96 hours	84 hours	N/A	60 to 96 hours	60 to 120 hours
Day 5	5 days	4 to 6 days	5 to 6 days	N/A
Day 30	30 days	15 to 60 days	15 to 60 days	N/A
Day 90	90 days	61 to 120 days	61 to 120 days	N/A

BI = Barthel Index; GOS = Glasgow Outcome Scale; mRS = modified Rankin Scale; Neuro-QoL = Quality of Life in Neurological Disorders; NIHSS = National Institutes of Health Stroke Scale.

* Assessed only at Day 90 Visit

All analyses of efficacy endpoints (primary, secondary, and exploratory) will be evaluated for superiority. Analyses will be adjusted for all or a subset of the following variables:

- Age (≤ 70 vs. > 70 years of age)
- Type of occlusion (ICA/M1 vs. M2)
- Baseline NIHSS (≤ 15 vs. > 15)
- Randomization site (ECC vs. nECC)
- Mechanical thrombectomy planned (Yes vs. No)
- Protocol version (Protocol V1-4 vs Protocol V5).

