In order to avoid small number of patients in the resulting strata, some variables may be removed from this list and not be adjusted for. The algorithm to perform this assessment is provided in [Appendix 5](#).

For endpoints that are based on the imaging data where both local and central reader's evaluation are collected, the central reader's evaluation will be used for analysis. Post-baseline final infarct volume will only be recorded by the central reader. The local recording for the baseline image will be used to calculate change from baseline in final infarct growth at 72-96 hours (or discharge if patient is being discharged prior to 72-96 hours visit).

Analyses of NIHSS, BI and GOS will only utilize data collected in-person or by telemedicine. NeuroQoL will only utilize data collected in-person. If any of these assessments are conducted by a mode that is not allowed for the assessment, the data will be listed, but excluded from analysis and not replaced by imputations.

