4.6.1 Primary Efficacy Endpoint

The primary endpoint is the ordinal mRS score at Day 90. mRS is an assessment of disability with values from 0 (no symptoms at all) to 5 (severe disability); death will be scored as a 6. During the study, mRS is collected at Baseline, Day 5 or hospital discharge, and 30 and 90 days after randomization. If death occurs prior to a scheduled assessment day, the mRS will be considered available and will be set to 6. The methodology for imputations related to the primary endpoint is described in Section [4.9.1.1](#).

The distribution of mRS at Day 90 will be summarized descriptively, and plotted using Grotta bars.

Analysis of the primary endpoint will test the hypothesis as follows:

$$H_0: OR_{\{TNK \text{ vs Placebo}\}} = 1 \text{ vs. } H_1: OR_{\{TNK \text{ vs Placebo}\}} \neq 1,$$

where $OR_{\{TNK \text{ vs Placebo}\}}$ stands for the overall odds ratio of achieving a lower level vs. higher level mRS between the tenecteplase and the placebo arms. Superiority of tenecteplase over placebo will be declared if the p-value of the estimated treatment effect is ≤ 0.003 (two-sided) at the efficacy interim analysis or ≤ 0.049 (two-sided) at the final analysis, after adjustment for one efficacy interim analysis.

In case there are issues with fitting the proportional odds model (such as e.g. a quasi-complete separation), the stratified Wilcoxon-Mann-Whitney Generalized Odds Ratio statistic (WMW GenOR) as described below will be employed. Otherwise, the proportional odds assumption will be tested. For this purpose, a proportional odds model will be fitted for the Day 90 mRS outcome, which will include treatment and adjusting variables. If the p-value for the overall score test of the proportional odds hypothesis is > 0.05 , the proportional odds assumption will be deemed acceptable. The assessment of the proportional odds assumption will be independent of the results from the primary efficacy analysis from the proportional odds model.

If the proportional odds hypothesis is not rejected, the parametric proportional odds model described above will be used to analyze the primary efficacy endpoint. The estimated common odds ratio of a lower mRS score (better outcome) will be presented for treatment (TNK vs. placebo). The corresponding Wald p-value and 95% CI will also be obtained.

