4.6.2.1 Functional Independence

A patient with functional independence is defined as having an mRS of 0–2 at Day 90. The proportion of patients with functional independence will be analyzed using logistic regression. The model will be adjusted as specified in Section 4.6. Observed counts and percentages for tenecteplase and placebo arms, and model based odds ratio, corresponding Wald 95% CI and p-value will be produced. This analysis will be performed with the same imputations used in the primary analysis (see Section 4.9.1).

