4.6.2.5 National Institutes of Health Stroke Scale

National Institutes of Health Stroke Scale is a questionnaire tool used to quantify the impairment caused by stroke. Scores are calculated by summing the responses on the survey, with higher values indicative of a more severe stroke. Missing responses will not be imputed and will result in a missing total NIHSS score. The range for the score is 0 to 42.

For this study, the NIHSS will be conducted at baseline, 24 hours, 72-96 hours, discharge or Day 5, 30 days, and 90 days. It will also be collected at the time of unscheduled imaging to support determination of sICH. All NIHSS scores will be allocated to analysis windows, and a single value per window will be selected for analysis according to the rules in Section 4.6. NIHSS score at Day 90 is a secondary endpoint.

NIHSS scores at each planned post-baseline time point will be summarized descriptively (mean, median, etc.). The van Elteren's test will be used to compare the distribution of tenecteplase and placebo arms, adjusting as specified in Section 4.6. The median treatment differences will be presented with 95% CI based on the Hodges-Lehmann approach for the location shift (median treatment difference).

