4.6.2.6 Barthel Index Score

The Barthel Index is an ordinal scale used to measure performance in activities of daily living (ADL). This 10-item scale describes ADL and mobility (e.g., feeding, bathing, grooming, dressing, bowel control, bladder control, toileting, chair transfer, ambulation, and stair climbing). Each performance item is rated on this scale with a given number of points assigned to each level or ranking. BI scoring ranges from 0 to 100, and lower scores representing greater dependency.

The proportion of patients with a BI score ≥ 95 at Day 90 will be analyzed using logistic regression adjusted as specified in Section 4.6. Observed counts and percentages for

tenecteplase and placebo arms, and model based odds ratio, corresponding Wald 95% CI and p-value will be produced.

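### The SAP gives no death rule for Day 90 Barthel Index ≥95 (testing order 6); under its defaults patients who die without an in-window value leave the test, so it compares survivors

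*SAP*

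**What the plan says.** SAP Section 4.6.2 tests the secondary endpoints in sequence once the primary succeeds. Day 90 NIHSS is order 5, Day 90 BI ≥95 is order 6 and good recovery on the Glasgow Outcome Scale (GOS) is order 7.

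Death is scored for these Day 90 scales:

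- mRS (Section 4.6.1): "If death occurs prior to a scheduled assessment day, the mRS will be considered available and will be set to 6".
- Functional independence (Section 4.6.2.1): "This analysis will be performed with the same imputations used in the primary analysis", so deaths count as not independent.
- GOS (Section 4.6.2.7): "If death occurs prior to Day 90, GOS will be considered available and will be set to 5", the worst category after the scale is reversed.

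For infarct volume (Section 4.6.3.2), an exploratory endpoint, the SAP excludes early deaths and says so.

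Section 4.6.2.6 on the BI describes the scale, "BI scoring ranges from 0 to 100, and lower scores representing greater dependency", and specifies logistic regression for the proportion at or above 95. It says nothing about death, and the instrument has no death category. Protocol Section 6.4.2 and Appendix 4 add no rule. Death is not among the intercurrent events named in SAP Section 4.6, which are planned thrombectomy not performed and COVID-19 infection.

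Two defaults then apply. Section 4.9: "Missing data will be maintained as missing in the analysis datasets, unless specified otherwise". Section 4.6, with an exception only for carrying mRS forward: "Assessments that are outside of the defined windows will not be used in analysis". The Day 90 window for the BI is 61 to 120 days.

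**The concern.** A logistic regression omits records with no outcome. On the written defaults, patients who die without an in-window BI value therefore leave an analysis that Section 4.1.1 places in the ITT population. What remains is a comparison of survivors. Survival is itself an outcome that treatment may change, and the sample-size table assumes that it does, so randomisation no longer protects the comparison.

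The wording also allows a second reading, in which the proportion is taken over all patients and a dead patient has not reached 95. The two readings give different denominators, estimates and p-values for an endpoint in the formal testing sequence. A failure at order 6 also stops the GOS test at order 7, where deaths are counted. If the choice is left until after unblinding, it can be challenged as data-driven.

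**Working it through.** **1. Who is affected.** Protocol Appendix 1 schedules the BI at discharge/Day 5, Day 30 (±7) and Day 90 (±14). The earliest scheduled value in the 61–120 day window is therefore at 90 − 14 = day 76. A patient who dies before day 76 has no scheduled in-window value. A patient assessed in the window who dies later keeps that value.

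**2. Inputs.** From SAP Section 2.3 and Table 1: 432 evaluable patients (216 per arm), two-sided alpha 0.049 (z = 1.969), and these mRS 0–6 distributions:

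- tenecteplase 17/20/16/15/13/7/12%
- placebo 13/13/12/14/18/12/18%

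Death is mRS 6, so planned mortality is 12% vs 18%.

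**3. The plan's own figure.** For the Wilcoxon-Mann-Whitney test, P(tenecteplase better) + ½P(tie) = 0.590. The tie-corrected null SE is √[(1 − 0.0216)/12 × 2/216] = 0.0275. Then 0.0896/0.0275 = 3.26, and Φ(3.26 − 1.97) gives 90.2% (90.5% with the variance under the alternative). The stated figure is at least 90%, so the inputs are read correctly.

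**4. Patients lost.** 216 × 0.12 = 25.9 and 216 × 0.18 = 38.9, about 65 of 432 (15%). This is an upper figure, because it assumes that none of them had an in-window value.

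**5. Effect on the BI test at planned mortality.** The documents give no BI distribution, so mRS 0–2 and mRS 0–1 are used as assumed stand-ins for BI ≥95. Success counting deaths as failures is p; among survivors it is p/(1 − mortality):

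- mRS 0–2: 53% vs 38% becomes 0.53/0.88 = 60.2% vs 0.38/0.82 = 46.3%.
- mRS 0–1: 37% vs 26% becomes 42.0% vs 31.7%.

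Power = Φ[(|p₁ − p₂| − z·s₀)/s₁], with s₀ the pooled SE and s₁ the unpooled SE. Survivors number 190.1 and 177.1.

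| Stand-in | Deaths | Calculation | Power |
|---|---|---|---|
| mRS 0–2 | counted | (0.150 − 1.969 × 0.0479)/0.0474 = 1.18 | 88% |
| mRS 0–2 | dropped | (0.1389 − 1.969 × 0.0521)/0.0516 = 0.70 | 76% |
| mRS 0–1 | counted | (0.110 − 1.969 × 0.0447)/0.0444 = 0.50 | 69% |
| mRS 0–1 | dropped | (0.1034 − 1.969 × 0.0504)/0.0500 = 0.08 | 53% |

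**6. Same survivors, equal mortality.** Keep the survivor distributions and set deaths to 15% in both arms (an assumption). Counted success is then 0.85 × the survivor proportion: 51.2% vs 39.4%, or 35.7% vs 27.0%. Survivors number 183.6 per arm.

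| Stand-in | Deaths counted | Deaths dropped |
|---|---|---|
| mRS 0–2 | 69% | 76% |
| mRS 0–1 | 50% | 53% |

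The ordering reverses. What stays the same across steps 5 and 6 is that the two rules test different quantities.

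**The case against.** **The ITT statement covers it.** Section 4.1.1 defines who belongs to the population. It does not assign an outcome to someone who has none.

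**A proportion of patients already counts deaths as failures.** This is a fair reading, and under it nothing is lost. A reader might infer that the SAP definitely drops deaths from the BI test, but the documents do not go that far: dropping them is the result of the defaults, not a stated rule. Good recovery on the GOS is also worded as a proportion of patients, however, and the SAP still gave it a death sentence. The ambiguity therefore stands.

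**Dropping deaths does not always cost power.** Correct, as step 6 shows. A reader might infer from the planned mortality alone that the default weakens the test; that holds only when deaths differ by arm roughly as planned. The mRS stand-in also matters: with mRS 0–2, the death-counted BI is simply functional independence again.

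**NIHSS at order 5 has the same gap.** It is tempting to extend the criticism. "NIHSS score at Day 90 is a secondary endpoint", and it has no death score either. But it is a rank comparison, missing responses are explicitly not imputed, and the defaults lead to one determinate survivors-only test. Choosing between that and a worst rank for death is a choice of estimand, not an error.

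**The mode-of-collection rule shows that deaths are meant to be left out.** The sentence in Section 4.6, "the data will be listed, but excluded from analysis and not replaced by imputations", concerns assessments done by a disallowed mode. It covers GOS too, which has a death rule, so it is no evidence either way.

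**Deaths are reported elsewhere.** Mortality to Day 30 and Day 90 and overall survival are both planned. That informs the reader but does not settle what the order 6 test compares.

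**Conclusion.** The concern holds for the Barthel Index. A sequentially tested endpoint lacks the death rule that the SAP gives to the mRS, functional independence and GOS, and the written defaults turn it into a comparison of survivors. Up to about 26 vs 39 of 216 patients per arm are affected at the planned mortality.

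The difference between the two rules is 12 to 16 percentage points of power in favour of counting deaths at 12% vs 18% mortality, and 3 to 7 points the other way at 15% in both arms. These powers are illustrative: they rest on mRS as a stand-in for BI, unadjusted two-proportion tests, and order 6 taken alone without the earlier steps. Only the mortality, sample size and alpha come from the plan.

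The primary analysis and order 1 are unaffected. A reader might infer a raised risk of a false claim of benefit. The documents do not establish that, since the mRS primary and functional independence, both of which count deaths, must succeed first. This should be fixed, but it does not threaten the trial's main conclusion.

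**What to change.** - **BI (Section 4.6.2.6).** State that a patient who dies before the Day 90 assessment is counted as BI not ≥95. Report BI among survivors as supportive.
- **One death trigger.** Use the same one for mRS, GOS and BI. At present Section 4.9.1.1 refers to death before the Day 90 visit is completed, whereas Section 4.6.2.7 refers to death before Day 90. A patient who dies on day 95 before the visit would be handled differently under the two.
- **NIHSS (Section 4.6.2.5).** Label the Day 90 test as survivors-only and show deaths by arm beside it.

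The cost is a few sentences and one derivation flag, with no new data, because death dates already feed the mRS rule and the survival analysis. The downside is that BI becomes a composite of death and dependency, which is why the survivors-only result should stay as supportive. The change belongs before database lock and unblinding, the point that SAP Section 1 sets for finalising the plan.
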